5.3. Data sources that will be used to collect data about subjects:¹⁰

Measures	Description	T1	T2	T3	Rater
Family Information Form	Parents report on demographic and socioeconomic information, and adolescent health history.	X			Parent
Pediatric Pancreatitis Questionnaire	Parents report on acute/chronic pancreatitis clinical history and diagnosis.	X			Parent
Pain Intensity, frequency, and duration	Pain intensity will be rated on the online diary using an 11-point NRS. Pain frequency and duration are averaged over each seven-day measurement period.	X	X	X	Child
Child Activity Limitation Interview (CALI-9)	Daily diary version of the CALI-9 will be used to rate perceived difficulty in completing 9 daily activities as a measure of pain-related disability.	X	X	X	Child
PROMIS Pediatric Emotional Distress Scales	8-item scale of anxiety that assesses fear (e.g., fearfulness), anxious misery (e.g., worry) and hyperarousal (e.g., nervousness) and 8-item scale of depressive symptoms.	X	X	X	Child
Pain Self-Efficacy	The Pain Self-Efficacy Scale is a 7-item measure that assesses the child's beliefs in carrying out activities when in pain. The scale has demonstrated good internal consistency, cross-informant reliability with parent report, and strong construct validity.	X	X	X	Child
PROMIS Pain interference	Pediatric Short Form assesses pain-related interference	X	X	X	Child
Bath Adolescent Pain Questionnaire–Parent Impact	Assesses changes in perception of burden, family functioning, and emotional distress associated with parenting youth with chronic pain.	X	X	X	Parent
Health-related quality of life	Pediatric Quality of Life Inventory will assess broad impact of health on child and family	X	X	X	Parent, Child
Health services utilization	Client Services Receipt Inventory for Pain assesses inpatient and outpatient visits, medications, other treatments, and indirect costs as reported by the parent	X		X	Parent
Treatment satisfaction and engagement	Treatment satisfaction (10 item measure with Likert ratings and open-ended items about content and delivery method) (P, A); Web usage		X		n/a

	(logins, completion of assignments, etc.) collected from the administrative website				
Adverse events	Adverse event form will be used.		X	X	Parent, Child
Abdominal Pain Index	Assesses child abdominal pain frequency, duration, and intensity.	X	X	X	Parent, Child

Information collected from INSPPIRE 2 study will be used in this study. This information includes information about abdominal pain, frequency and severity of pancreatitis attacks, treatments used, hospital and emergency room visits, and blood draw for testing subjects' CP genetic variants. This information will not be collected for community participants who are not involved in INSPPIRE2.

5.4. Data to be collected, including long-term follow-up data:¹¹

Data will be collected at three time points. Assessments will occur at baseline (T1), immediately after intervention (about 2 months; T2), and repeated at 6 months postintervention (T3).

6. Data and Specimen Banking¹²

6.1. Complete list of the data and/or specimens to be included in the bank:¹³

N/A

6.2. Location of data and/or specimen storage:¹⁴

N/A

6.3. List of those with direct access to data and/or specimens in the bank:

N/A

6.4. Length of time data and/or specimens will be stored in the bank:

N/A

6.5. Procedures for protecting the confidentiality and privacy of the subjects from whom the data and/or specimens were collected:¹⁵

N/A

6.6. How the data and/or specimens will be made available for future use:

N/A

6.6.1. Who can request data and/or specimens from the bank:

N/A

6.6.2. Format in which data and/or specimens will be provided:

N/A

6.6.3. Process for investigators to request data and/or specimens:¹⁶

N/A

6.6.4. Restrictions on future use:¹⁷

N/A

6.6.5. Plan for providing data results from banked data/specimens:

N/A

7. Sharing of Results**7.1. Plan to share results with subjects/others:¹⁸**

Study results will be shared with all enrolled participants after active participant study involvement is complete and study analyses are finished. These results would be in the form of a one-time letter outlining study findings (sent via email).

8. Study Timelines**8.1. Duration of an individual subject's participation in the study:**

Approximately 9 Months

8.2. Duration anticipated to enroll all study subjects:

Approximately 3 years

8.3. Estimated date for the investigators to complete this study:

This will be a 5 year study so approximately Winter 2024

9. Study Population¹⁹**9.1. Inclusion criteria for each subject population (e.g., patients, parents, providers):**

Study participants in the RCT will include 260 children with chronic or acute recurring pancreatitis, along with one participating parent/caregiver. Youth age 18 or 19 can enroll in the study even if they do not have a parent/primary caregiver who can participate. Inclusion criteria include: (a) diagnosis of CP or ARP, (b) ages 10-19 years, (c) at least 4 AP flare-ups/attacks in past year, or at least 1 instance of moderate (4/10 pain) pancreatitis/abdominal pain in the past month, and (d) access to the Internet on any web-enabled device.

9.2. Exclusion criteria for each subject population:

Exclusion criteria include parent report of the following: (a) non-English speaking, (b) inability to read at the 5th grade level due to learning or developmental delays; (c) children with cystic fibrosis who have pancreatic insufficiency at the time of diagnosis; (d) patients with Shwachman-Bodian-Diamond Syndrome; (e) ARP with no evidence of chronic or persistent pain. (f) anticipated surgery (TPIAT or other) during study participation (6 month timeframe); (g) other severe systemic disease.

9.3. Vulnerable populations involved in the study:²⁰☒ **Children/Teenagers²¹**

Risk assessment specific to this vulnerable population and additional safeguards:²²

The research is considered minimal risk as the probability and magnitude of psychological and physical risks anticipated in this research are not greater than those ordinarily encountered in daily life or during the performance of routine physical or psychological examinations or tests. The relaxation skills and pain coping strategies taught in the online program is comparable to what is taught within clinical programs. The participant has the option of withdrawing participation at any time during the study. Knowledge gained through this research will guide future research and interventions to help adolescents with chronic pancreatitis.

- ☐ Children who are Wards of the State²³

Risk assessment specific to this vulnerable population and additional safeguards:

N/A

- ☐ Adults Unable to Consent²⁴

Risk assessment specific to this vulnerable population and additional safeguards:

N/A

- ☐ Neonates of Uncertain Viability or Non-Viable Neonates²⁵

Risk assessment specific to this vulnerable population and additional safeguards:

N/A

- ☐ Pregnant Women²⁶

Additional safeguards:

N/A

- ☐ Prisoners²⁷

Additional safeguards:

N/A

10. Number of Subjects

- 10.1.** Total number of subjects to be enrolled locally:²⁸

30 dyads- children with CP/ARP and their parents/caregivers (if available)

- 10.2.** Total number of subjects to be enrolled across all participating sites:²⁹

260 dyads- children with CP/ARP and their parents/caregivers (if available)

- 10.3.** Number of screened subjects versus the actual number enrolled in the research:³⁰

We anticipate that screening 381 children with CP/ARP will enable us to enroll 260 into this study.

- 10.4.** Power analysis:

Based on our historical data, the estimate of the standard deviation for the primary outcome pain-related disability is approximately 4. We expect a difference of 1.5 between WebMAP and WebED in the mean score of pain-related disability. At the significance level of 0.05, we need 112 subjects per group to have 80% power to detect a difference. Results indicate sufficient power to detect relatively small differences between children receiving WebMAP compared to WebED. Taking into account 10-15% attrition, we will enroll 130 patients per group. Because Aims 2 and 3 employ the LMM regression approach, the power calculation is complicated and requires re-specifying model parameters that are virtually unknown a priori. Therefore, we take a simple approach based on correlation coefficient. Given the sample size of 112 subjects, we have 80% power to detect the correlation of 0.27 between gene (or baseline clinical characteristics) and pain-related disability, at the significance level of 0.05. As the LMM is more efficient, the actual power will be greater. Power to detect correlations between genetic/clinical characteristics and pain-related disability may be lowered depending on the number of community participants enrolled.

11. Withdrawal of Subjects

- 11.1.** Anticipated circumstances under which subjects will be withdrawn from the research without their consent:

The PI may decide to withdraw participants from the study if a family is not able to comply with study procedures or do not understand study instructions.

11.2. Procedures for orderly termination:

If a participant must be withdrawn from all study procedures the study staff would contact the family to explain the cause for study withdrawal and finalized study termination.

11.3. Procedures that will be followed when subjects withdraw from the research, including partial withdrawal from procedures with continued data collection and withdrawal from data/specimen banking:

Full Withdrawal: If a participant must be withdrawn from all study procedures the study staff would contact the family to explain the cause for study withdrawal and finalized study termination.

Partial Withdrawal: If a participant partially withdraws from the procedures, study staff would contact the family to discuss family's interest in participation. If the family is interested, the study procedures will be continued, if the family is not interested, this will be considered a full withdrawal.

12. Risks to Subjects

12.1. Reasonably foreseeable risks to subjects (include each study population, each arm, and optional procedures):

This study is minimal risk. There are potential risks around emotional distress, time commitment, and confidentiality. Although asking about physical symptoms and mood/behavior does not typically result in any distress, there is a small risk of emotional distress. There is a potential risk of loss of confidentiality.

12.2. Procedures with unforeseeable risks:

N/A

12.3. Procedures with risks to an embryo or fetus should the subject be or become pregnant:

N/A

12.4. Risks to others who are not subjects:

N/A

12.5. Procedures performed to lessen the probability or magnitude of risks:

Participants will be advised they can skip any questions they feel uncomfortable answering. To support confidentiality, adolescents will be asked to complete questionnaires independently. We will make every effort to protect this data. For example, all data will be coded with a unique ID number. Participants will be informed of their right to refuse to participate in any part of the data collection and given the phone numbers of the PI and the Seattle Children's IRB in the event that they desire further information or would like to issue a formal complaint.

13. Potential Benefits to Subjects

13.1. Potential benefits that individual subjects may experience from taking part in the research.³¹

Participation in this research study may or may not benefit the subject. The 8-week Web-MAP program may help to increase daily functioning and decrease pain intensity in children and teens who complete this program as it has shown effectiveness in other youth with chronic pain.

14. Data Analysis/Management

14.1. Data analysis plan, including statistical procedures:

Distributions of primary and secondary outcome variables at each time point (and on difference scores between time points) will be examined first with summary statistics and graphical tools. For outcome variables with highly skewed distributions, we will either apply transformation or non-parametric test procedures. Preliminary work will also involve computation of scale reliabilities (e.g., internal consistency using Cronbach's alpha) of all of the self report measures. The RCT analysis will be an intent-to-treat analysis including all randomized subjects. Two-sample t-test will be used to test the difference between the WebMAP group and WebED group in pain-related disability and other outcomes (e.g., anxiety, depression and HRQOL) at baseline, 2 months and 6 months. In the case that the outcome is categorical, the chi-squared test will be used. The pre-post change in pain-related disability will also be assessed within and between groups using one-sample or two-sample t-test. Linear mixed models (LMM) will be further used to compare the change in pain-related disability over time (from baseline to follow-ups) between WebMAP and WebED. The LMM is ideally suited for analysis of repeated measures because it allows for more specific estimation of the correlation structure of the residuals, it efficiently handles unbalanced designs and missing data, without excluding participants or imputing values. The repeated measures of pain-related disability will be treated as the dependent variable. Measurement time, intervention condition, and their interaction will be included in the LMM as covariates. We will include biological covariates of age and sex in all models and will include other demographic and clinical factors, as needed to adjust for potential confounding effects. Fit statistics (e.g., Akaike's Information Criterion) will be evaluated for all models to ascertain the best fit of the correlation structure of the dataset. We will use a computer program, PROC MIXED (SAS v9.3 SAS Institute Inc, Cary, NC) to estimate and test the models with continuous dependent measures. Results will be summarized with the estimates of model parameters and p-values. For a binary endpoint of clinically significant reduction in pain (i.e., achieved 50% or greater reduction in pain intensity), we will employ the generalized linear mixed model (GLMM) to model and compare the changes over time (from baseline to follow-ups) between WebMAP and WebEd. We will use SAS PROC GLMIX, which provides an adaptation to the LMM approach for categorical data.

Blood draw and collection will be done by the INSPPIRE 2 study, but will not be done for patients recruited from community organizations who are not participating in INSPPIRE 2. The data we need will be pulled from that study for analysis. LMM will be our primary analytic tool to investigate the association between genetic co-variants and treatment response in internet-based CBT. In the LMM, repeated measures of painrelated disability will be used as the dependent variable. The covariates include time, gene and demographic variables (e.g., sex) when necessary. In the initial evaluation, "genetic signatures" will be used as covariates. This approach markedly reduces complexity by combining known pathogenic variants in a class into an object such as "CFTR-related disorders", "Pathologic Trypsins", "Unfolded protein response (UPR)", "Lipotoxicity", "idiopathic" and "others" for etiology, as well as "opiate pharmacogenetics defect", "pain receptor" and others for modifiers. In addition, pathogenic variants with large effects (e.g. PRSS1 p.R122H, SPINK1 p.N34S) or high frequency (e.g. CTRC g.60G haplotype) will be evaluated as independent covariates. To investigate multiple genes and genetic signatures, we will conduct univariate gene analysis by regressing each gene independently on the pain-related disability outcome to see if there is reasonable signal of association between the gene and pain-related disability. Using this procedure, we screen out the genes with p value > 0.1. We then build

a multivariate model based on the genes with p value < 0.1 in the univariate analysis. In the case that the number of genes included in the multivariate model is still large, model selection (e.g., using LASSO) will be performed to obtain a parsimonious model and identify the genes that are significantly associated with the outcome pain-related disability. Further analysis utilizing machine learning programs for cluster analysis, such as principle component analysis, will be conducted as complementary and confirmatory analyses.

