2.2. Relevant preliminary data:¹

Evaluation of Web-Based Management of Adolescent Pain (WebMAP). [name] developed an Internet delivered CBT pain intervention called WebMAP that includes 8-10 weeks of online modules to teach relaxation skills, pain coping strategies, and parent behavioral and communication techniques to youth with mixed chronic pain conditions. In the initial RCT with 48 youth (11–17 years) with a variety of pain conditions (e.g., headache, stomachache, musculoskeletal pain), significant reductions in pain and disability were found for youth receiving WebMAP compared to a wait-list control group.⁵¹ Following up on this initial trial, [name] recently completed a second large multicenter RCT of WebMAP involving 273 adolescents (ages 11-17 years) with chronic pain and their parents from 14 centers in the U.S. and Canada 23. Adjunctive to treatment in pain clinic, youth were randomized to one of two Internet treatments, WebMAP (adolescent and parent CBT pain intervention, n=138) vs WebED (education control, n=135). Close tracking and monitoring procedures led to an excellent retention rate in the trial (94.2% post-treatment, 92.4% at 6-months, and 92.4% at 12-months), and superb compliance (> 80%) with both treatment conditions (education and CBT). In support of our primary hypotheses, youth receiving Internet CBT achieved greater improvement in pain-related disability compared to the Internet Education group from baseline to 6-month follow-up ($b = -1.13$, $p = 0.03$, $d = -0.25$). There were small effects of Internet CBT on improving depression in the Internet CBT group (relative to Internet Education) from baseline to post-treatment ($b = -0.59$, $p = 0.04$, $d = -0.09$). Similarly, adolescents receiving Internet CBT showed a significant reduction in pain-related anxiety relative to the Internet Education group from baseline to post-treatment ($b = -1.33$, $p = 0.04$, $d = -0.13$). As hypothesized, there were significant, small to medium effects of treatment on reducing maladaptive parent behaviors. Parents in the Internet CBT group demonstrated a significantly greater reduction in protective behaviors compared to the Internet Education group from baseline to post-treatment ($b = -0.26$, $p < 0.001$, $d = -0.49$) and from baseline to six-month follow-up ($b = -0.19$, $p = 0.001$, $d = -0.40$). Effects were maintained through the 12-month follow-up 26. WebMAP has been adapted and tested in several other pediatric painful disorders including a completed trial in chronic headache 25, sickle cell disease (Palermo, et al, in press) and an ongoing trial with 300 youth with functional abdominal pain (NIH R01HD076983, PI: [name]). Our data and experience so far confirm WebMAP as an efficient, easily accessible tool with great potential to reduce pain-related disability and parental maladaptive behaviors that perpetuate and sustain painful disorders.

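### No planned efficacy test conditions on the baseline CALI-9 score; a baseline-adjusted primary contrast gains precision at no cost, and 10.4 should also state power at the earlier trial's effect

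*Combined protocol and SAP*

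**What the plan says.** Section 10.4 (Power analysis) takes the SD from historical data: "the estimate of the standard deviation for the primary outcome pain-related disability is approximately 4". It gives the design difference without a source: "We expect a difference of 1.5 between WebMAP and WebED in the mean score of pain-related disability". It concludes: "At the significance level of 0.05, we need 112 subjects per group to have 80% power to detect a difference". It does not name the test behind this figure, and it does not say whether the SD is of the score at one time point or of the change.

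Section 2.2 reports the earlier multicentre trial of the same two programmes in 273 adolescents with chronic pain. The effect on pain-related disability was "from baseline to 6-month follow-up ($b = -1.13$, $p = 0.03$, $d = -0.25").

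Section 14.1 lists three kinds of between-group analysis for the primary outcome: two-sample t-tests at baseline, 2 months and 6 months; t-tests on pre-post change; and a linear mixed model (LMM) with the repeated disability scores as the dependent variable. On its terms: "Measurement time, intervention condition, and their interaction will be included in the LMM as covariates". Age and sex are added to all models. The T1 disability score is not named as a covariate. The table in section 5.3 schedules the CALI-9 diary at T1, T2 and T3.

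**The concern.** In a randomised trial with a baseline measure of the outcome, the contrast that conditions on baseline is at least as precise as the follow-up comparison and the change comparison, whatever the correlation. Section 14.1 plans the other two. The follow-up t-tests do not use T1. The change t-tests subtract T1 with a fixed coefficient of one. The LMM includes a condition term that leaves the arms free to differ at T1, so with complete data its condition-by-time contrast is a difference in mean change.

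This matters because the margin is thin. The design difference is 0.375 SD, and the only effect the protocol reports for these two programmes on this construct is 0.25 to 0.28 SD. If the true effect is nearer that benchmark, power is well below 80%, and a null result could be read as no benefit in chronic or acute recurrent pancreatitis. Precision available from data already being collected should not be left unused, and 10.4 should let the reader see how power depends on the assumed 1.5.

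**Working it through.** **Inputs.** Difference 1.5, SD 4, alpha 0.05, power 80%, 112 per group (10.4). Earlier effect 1.13 points, d = 0.25, p = 0.03 (2.2). Two-sided alpha is assumed, because it reproduces 112 (one-sided gives 88). The T1-to-follow-up correlation r is not in the documents; 0.4 to 0.7 is assumed.

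**Reproducing the plan's figure.** n = 2(1.96 + 0.8416)² × 4² / 1.5² = 111.6, so 112 per group. The noncentral t gives 112.6 and power of 79.8% at 112. The arithmetic is sound and matches an unadjusted two-sample comparison.

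**Unadjusted power at the earlier effect.** The result can be scaled in two ways: d = 0.25 as reported, or 1.13/4 = 0.2825 using this trial's SD. With 112 per group (noncentral t), power is 46.1% and 55.8%. With all 130 analysed it is 51.9% and 62.1%.

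**Cross-check without an assumed SD or r.** p = 0.03 gives z = 2.17, so the standard error was 1.13/2.17 = 0.52. Suppose 252 (92.4% of 273) to 273 were analysed. Rescaled to 224, the standard error is 0.55 to 0.57 and power for 1.13 is about 50-53%.

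**Variance of each contrast**, one follow-up time, equal variances at T1 and follow-up, in units of the cross-sectional variance:

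- Follow-up t-test: 1
- Change t-test, or LMM with a free condition effect at T1: 2(1 − r)
- Baseline-adjusted: 1 − r²

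The ratio of adjusted to change is (1 − r²)/[2(1 − r)] = (1 + r)/2, which is 0.70 at r = 0.4, 0.75 at r = 0.5 and 0.85 at r = 0.7. Hence 30%, 25% and 15% less variance.

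**Power at 112 per group**, SD 4 taken as cross-sectional (noncentral t; planned change contrast → baseline-adjusted):

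| r | d = 0.25 | 1.13 / SD 4 | 1.5 / SD 4 |
|---|---|---|---|
| 0.4 | 39.8% → 52.9% | 48.5% → 63.2% | 72.3% → 86.2% |
| 0.5 | 46.1% → 57.6% | 55.8% → 68.1% | 79.8% → 89.7% |
| 0.7 | 67.2% → 74.2% | 77.6% → 83.8% | 95.0% → 97.5% |

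The follow-up t-test stays at 46.1%, 55.8% and 79.8% whatever r is. The change contrast beats it only when r exceeds 0.5.

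**If SD 4 is instead the SD of change**, the planned change contrast has 46.1% at d = 0.25 for every r. Adjustment gives 60.5% at r = 0.4, 57.6% at r = 0.5 and 52.4% at r = 0.7.

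**The case against.** The strongest reply is that the plan already has an LMM, so the gain must be measured against that and not against the follow-up t-test. This stands, and the table above does so. At r = 0.7 the gain is about 6 to 7 points, because the change contrast already captures most of the information. A reader might infer that the plan throws the T1 score away; it does not, since the change t-tests and the LMM both use it, only less efficiently. The remark in 10.4 that the LMM is more efficient does not settle the matter, because it is made for Aims 2 and 3.

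A reader might also infer that the design has only 46-56% power. The documents do not support that. This is the unadjusted power at one benchmark, which comes from mixed chronic pain at ages 11-17. Section 2.2 does not say that its disability score is the CALI-9 diary or which SD underlies d. The historical data cited in 10.4 need not be that trial alone.

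Two further inferences fail. The first is that the attrition allowance is wrong. The plan says: "Taking into account 10-15% attrition, we will enroll 130 patients per group". That leaves 130 × 0.90 = 117 to 130 × 0.85 = 110.5, which straddles 112. Power at 110 is 79.1%, and the 92.4% six-month retention in section 2.2 would leave about 120. No stated figure needs correcting. The second is that the following sentence is false: "Results indicate sufficient power to detect relatively small differences between children receiving WebMAP compared to WebED". The design effect is 0.375, and section 2.2 calls effects that include 0.40 to 0.49 small to medium, so the adjective fits the document's own usage.

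Finally, 10.4 names no test. An unadjusted comparison is inferred from the exact reproduction of 112 and from 14.1.

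**Conclusion.** The point holds as an avoidable loss of precision and an incomplete power statement. It is not a sample-size error. None of the efficacy tests in 14.1 conditions on the T1 CALI-9 score. A contrast that does has 15-30% less variance than the planned change contrast over r = 0.7 to 0.4. At 112 per group this adds roughly 6 to 15 points of power at the earlier trial's effect, and about 10 points at the design difference when r = 0.5.

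The variance ratio depends only on r and on equal variances at T1 and follow-up. The power figures also depend on SD 4 being cross-sectional, which 10.4 does not say. Recovery is partial: within the assumed range, 80% power at the earlier effect is reached only near r = 0.7, and only on the 1.13/SD 4 scaling.

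**What to change.** In 14.1, name one baseline-adjusted primary between-group contrast for pain-related disability, in place of the t-tests and the unconstrained arm-by-time contrast. Either of these serves:

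- an LMM on the T2 and T3 scores with the T1 CALI-9 score as a covariate, plus time, condition and their interaction; or
- an LMM on T1, T2 and T3 with a common T1 mean for both arms (no condition effect at T1).

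The t-tests can remain as descriptive or supporting analyses.

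In 10.4, state that 80% power applies to a 1.5-point difference with SD 4 (d = 0.375), and say whether that SD is cross-sectional or of change. Add that at the effect seen in the earlier trial of the same programmes (1.13 points, d = 0.25; a benchmark from a mixed chronic pain population) unadjusted power at 112 per group is about 46-56%. If a figure for the adjusted analysis is given, state the assumed r and show a range.

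The cost is protocol and SAP wording and a less favourable figure on the page. No extra participants, visits or data are needed. The change should be made before anyone sees outcome data by arm.
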